5.3.4 Respiratory comorbidity and allergies

Respiratory comorbidities other than COPD or asthma will be conditions recorded at any time before or up to 30 days after index date and will be ascertained using the diseases and codes listed in [Table 9](#). These will be described for the purpose of characterising the study population overall and the subgroup of patients classified as potential off-label users, but do not constitute “suspected off-label indications.”

Table 9 Respiratory comorbidity and allergies

Disease description ¹	ICD-10 code	ICPC code
Pneumonia	J09-J18	R81
Allergic rhinitis	J30	R97
Bronchiectasis	J47	—
Lung diseases due to external agents	J60-J69	—
Acute bronchitis or bronchiolitis ²	J20, J21, J22, J40	R78
Other respiratory conditions	J80-J99	R99

COPD = Chronic Obstructive Pulmonary Disease; ICD-10 = *International Statistical Classification of Diseases and Related Health Problems, 10th Revision*; ICPC = *International Classification of Primary Care*.

¹ Other respiratory comorbidities of interest may be described depending on data availability.

² The use of ICD-10 code J40 “Bronchitis, not specified as acute or chronic” will be assessed in the data source-specific definitions.

5.3.5 Other comorbidities

Characterisation of the patient population will include a description of the medical history of comorbidities listed in [Annex Table 1-5](#), which will be identified through recorded diagnosis at any time before or on the index date. Additional details on database-specific specifications are described in Section [9.2](#).

5.3.6 Comedications

Characterisation of the patient population will include a description of the prescriptions or dispensings for comedications of interest listed in [Annex Table 1-6](#) that are recorded within 12 months before or on the index date.

6. GENERAL ANALYSIS DEFINITIONS

6.1 EXPOSURE

The main study exposures of interest are olodaterol and indacaterol. New users of olodaterol and indacaterol will be identified at the first record of a prescription/dispensing for the relevant medication code specific to each database within the study period (see [Table 1](#) for study periods in each data source).

For these medications, the following characteristics will be described:

- *Daily dose at the index date* (µg): the dose prescribed by the physician at the index date, when available, or ascertained by the dispensed defined daily dose (DDD) and the estimation of the daily dose at index date. The estimated daily dose dispensed at the index date will be calculated using the recorded information on strength and quantity dispensed and the days of supply of the first prescription for olodaterol and indacaterol. Missing values for dose are expected and will be described.
- *Number of packages at the index date*: the number of packages prescribed by the physician, when available, or ascertained by the dispensed DDD. The estimated number of packages dispensed at the index date will be calculated using the recorded information on quantity dispensed and/or the days of supply of the first prescription for olodaterol and indacaterol. Missing values for dose are expected and will be described.

Information of interest to identify the drugs of interest and the daily dose and the number of packages at the index date is described in [Table 10](#).

Table 10 Information on olodaterol and indacaterol

Descriptor	Indacaterol	Olodaterol
Brand name	Onbrez Breezhaler (Hirobriz Breezhaler and Oslif Breezhaler in The Netherlands)	Striverdi Respimat
ATC	R03AC18	R03AC19
Formulation	Inhalation powder	Solution for inhalation
Presentation	Capsules	Cartridges
Strengths	150 mcg and 300 mcg	2.5 mcg
Package size	30 capsules	60 cartridges
DDD	150 mcg	5 mcg
Recommended dose	150 mcg once a day	2 puffs of 2.5 mcg once a day
Maximum dose	300 mcg once a day	5 mcg once a day

ATC = Anatomical Therapeutic Chemical; DDD = Defined Daily Dose.

Source: Onbrez Summary of Product Characteristics [\[R16-2634\]](#); Striverdi Summary of Product Characteristics [\[R16-2633\]](#); WHO Collaborating Centre for Drug Statistics Methodology. ATC/DDD Index 2015. Available at: https://www.whocc.no/atc_ddd_index/.

Proprietary confidential information © 2017 Boehringer Ingelheim International GmbH or one or more of its affiliated companies

Additional details on the database-specific definitions of the exposure variables in each data source are described in Section [9.2](#).

6.2 IMPORTANT PROTOCOL VIOLATIONS

None.

6.3 PATIENT SETS ANALYSED

Patients in the study will be required to meet the following criteria, as ascertained from each of the data sources:

- Receive a first dispensing for single-agent formulations of olodaterol or indacaterol during the study period with no prescriptions/dispensings ever before (see study period in [Table 1](#))
- Have at least 1 year of continuous enrolment in the data source immediately preceding the index date
- Have available data and no implausible values for age (< 0 years and > 120 years) or sex

Two study medication groups will be created: (1) a group of new users of olodaterol and (2) a group of new users of indacaterol. Inclusion in the study cohort as a new user in one of the two groups does not preclude the patient from being included as a new user in the other group if the inclusion criteria are met. The number of patients included in both groups will be reported.

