### 9.2.3 Study groups

Study groups are those subjects from the source population who (1) receive a first dispensing for single-agent formulations of olodaterol or indacaterol and (2) have at least 12 months of continuous enrolment in the study databases preceding the index date. Two study groups will be created: (1) a group of new users of olodaterol and (2) a group of new users of indacaterol.

New users of olodaterol are defined as patients who, with at least 12 months of continuous enrolment before the index date, have their first record of a dispensing for olodaterol. Similarly, new users of indacaterol have their first record of a dispensing for indacaterol in the database (after at least 12 months of continuous enrolment). Patients who receive a dispensing for olodaterol or indacaterol before they meet the criteria of 12 months of continuous enrolment in the database are not eligible to enter the corresponding study groups (olodaterol or indacaterol).

Each group of new users of olodaterol and new users of indacaterol will be divided into two subgroups: (1) LABA naïve in the short term (3 months) and (2) switchers from another LABA. Patients who are LABA naïve in the short term are defined as any new users of olodaterol or indacaterol who did not receive any dispensing for LABAs within 3 months

before the index date. Switchers are defined as any new user of olodaterol or indacaterol who received a dispensing for a different LABA within the 3 months before the index date. Within the olodaterol group and within the indacaterol group, LABA-naïve patients and switchers will be described and compared.

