### 9.3 VARIABLES

#### 9.3.1 Exposures

New users of olodaterol and indacaterol will be identified at the first record of a dispensing for the relevant medication code specific to each database. New users are defined in Section 9.2.3. The ATC code for indacaterol is R03AC18, classified as a selective beta2-adrenoreceptor agonist in the category of inhalant adrenergics. Indacaterol is available as inhalation powder with a defined daily dose (DDD) of 0.15 mg. The ATC code for olodaterol is R03AC19.

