Very severe	Occurrence of at least one of the following events in the 12 months before the index date unless another time period is specified: 
 • Dispensed oxygen therapy^{1,2} • Dispensed nebuliser therapy^{1,2} • Diagnosis of emphysema at any time before the index date¹

COPD = Chronic Obstructive Pulmonary Disease.

- 1 Severity criteria also included in definition from Curkendall et al., 2006 [[P07-09136](#)].
- 2 Severity criteria also included in definition from Soriano et al., 2001 [[R08-1492](#)].
- 3 Severity criteria modified to align with the Global Initiative for Chronic Obstructive Lung Disease (GOLD) 2016 definition for severity categories C and D [[P16-00121](#)]. If two or more of these criteria occur within a 21-day time period, they will be considered part of the same exacerbation episode and counted only once. If one or more of these criteria occur within a 21-day period of a hospitalisation for COPD, this will be considered part of the same “COPD exacerbation with hospitalisation” episode.

Sources: modified from Verhamme et al., 2012 [[P11-13226](#)]; Soriano et al., 2001 [[R08-1492](#)]; Curkendall et al., 2006 [[P07-09136](#)]; and GOLD, 2016 [[P16-00121](#)].

Because data on hospitalisations are not available in the IMS RWE LPD database, COPD severity will not be described in this database.

The proposed operational definitions to be applied when assessing the severity of COPD are as follows:

- Same-class “drugs for obstructive airways disease”: medications listed in [Annex Table 1-6](#) will be identified through prescriptions/dispensings for the list of medications of interest recorded in the database within 12 months before or on the index date and classified into one of the following drug classes:
 - Bronchodilators: inhaled short-acting muscarinic antagonists (SAMAs), inhaled LAMAs, inhaled short-acting beta2-agonists (SABAs), inhaled LABAs, and fixed combinations of SABAs and SAMAs
 - Inhaled glucocorticosteroids: ICS alone, fixed combinations of SABAs and ICSs, and fixed combinations of LABAs and ICSs
 - Systemic glucocorticosteroids
 - Systemic beta2-agonists
 - Xanthines
 - Roflumilast
- Hospitalisation for COPD exacerbation: an inpatient (primary or secondary discharge) code for COPD (ICD-10 codes: J41-J44), acute bronchitis (ICD-10 codes: J20, J21, J22, J40), or pneumonia (ICD-10 codes J09, J18) within 12 months before or on the index date.

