Annex Table 1-6 (cont'd) Anatomical Therapeutic Chemical codes for comedications

Medication description	ATC code
Drugs for musculoskeletal system	M01A, N02BA, M01B, M01C
Antidepressants	N06A
Antineoplastic agents	L01
Immunosuppressants	L04
Antivirals for systemic use	J05
Hormone-replacement therapy: Estrogens, progestogens, and estrogens in combination	G03C, G03D, G03F
Drugs used in nicotine dependence	N07BA

ATC = Anatomical Therapeutic Chemical; ICS = Inhaled Glucocorticosteroid; LABA = Long-Acting Beta2-Agonist; LAMA = Long-Acting Muscarinic Antagonist; SABA = Short-Acting Beta2-Agonist; SAMA = Short-Acting Muscarinic Antagonist.

1 The national drug code of each database country will be used to identify medications without an individual ATC code.

Source: WHO Collaborating Centre for Drug Statistics Methodology. ATC/DDD Index 2013. Updated 20 December 2012. Available at: [website: whooc.no/atc_ddd_index/](http://website.whooc.no/atc_ddd_index/). Accessed 21 January 2013.

Proprietary confidential information © 2017 Boehringer Ingelheim International GmbH or one or more of its affiliated companies

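### SAP Annex Table 1-6 has no LABA/LAMA fixed-combination class and no code for olodaterol, so prior maintenance treatment can be recorded as none; separately, SAP 6.3 leaves open what its look-back covers

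*SAP*

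**What the plan says.** **Entry.** SAP 6.3 asks that a patient "Receive a first dispensing for single-agent formulations of olodaterol or indacaterol during the study period with no prescriptions/dispensings ever before". SAP 6.1 explains how such starters are found: "identified at the first record of a prescription/dispensing for the relevant medication code specific to each database within the study period". The only codes supplied are those in SAP Table 10, the same as in Protocol 9.3.1. For the comparator the protocol states "The ATC code for indacaterol is R03AC18"; for the study drug it states "The ATC code for olodaterol is R03AC19". Protocol 9.2.3 likewise ties entry to the first single-agent dispensing and asks for a year of prior enrolment.

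**Prior medication.** SAP Annex Table 1-6 supplies the lists for comedications (5.3.6), total and respiratory dispensings (Table 7), the severity drug classes (5.3.3) and probable COPD (5.1). Its fixed inhaled combinations are LABA/ICS, SABA/SAMA and SABA/ICS. In 5.3.3 the bronchodilator class contains the four single-agent groups plus SABA/SAMA, and the steroid class reads "Inhaled glucocorticosteroids: ICS alone, fixed combinations of SABAs and ICSs, and fixed combinations of LABAs and ICSs". LABA/LAMA appears in neither place.

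**Dates of the lists.** The annex cites "ATC/DDD Index 2013. Updated 20 December 2012". Table 10 cites "ATC/DDD Index 2015". SAP Table 1 runs the study from 2014 to Q4 2016 in the Netherlands and Denmark, and from October 2015 to Q4 2017 in France.

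**Subgroups.** SAP Section 7 stratifies all analyses by LABA-naïve patients and switchers. Protocol 9.2.3 defines the first by no LABA dispensing in the 3 months before index, and the second by a different LABA in that window.

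**The concern.** SAP 5.1 expressly admits combinations when it defines probable COPD, then sends the programmer to a list without one whole class of them. SAP 6.5 says that whatever is not recorded is treated as absent and leads to misclassification, not to missing values. An omitted class would therefore leave no trace in the output tables: treated patients would appear untreated.

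Three descriptions are at stake: COPD severity, prior respiratory treatment, and the breakdown of adults with no recorded COPD or asthma. The last matters most in Denmark, where SAP Table 2 shows no general practitioner diagnoses, so medication history is a main clue to undiagnosed COPD.

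Section 6.3 raises a different question. A patient who moves from a combination product to the single-agent product with the same LABA is new to the product but not to the substance. The plan neither counts such patients nor says whether its rule removes them.

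**Working it through.** **1. What the gap does, rule by rule.** Take a regular user whose only respiratory drug in the year before index was a LABA/LAMA combination.

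| Rule | As written | With the class listed |
|---|---|---|
| Severity (SAP Table 8), COPD recorded, no severe or very severe criterion | Fewer than two dispensings of a listed class: mild | At least two, no more than 6 months apart: moderate |
| Probable COPD (5.1), adult with no COPD or asthma diagnosis, two or more prescriptions after age 40 and none before | Not met. With no other respiratory condition, the patient falls in the residual row of 7.5.1 | Met |
| Respiratory dispensings (Table 7) | 0 | Actual count |
| LABA-naïve or switcher, combination dispensed within 3 months | LABA-naïve, if the annex is the LABA list | Not LABA-naïve |

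The severity error affects only the boundary between mild and moderate. It arises only in PHARMO and Denmark, because 5.3.3 does not describe severity in the French database.

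**2. The missing olodaterol code.** The Table 7 footnote says indacaterol dispensings are counted in the olodaterol cohort and the reverse. R03AC18 is in the annex (under inhaled SABAs) and R03AC19 is not. Taken literally, prior indacaterol is counted in the olodaterol cohort, but prior olodaterol is not counted in the indacaterol cohort.

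**3. What the gap does not do.** Section 7.5.1 assigns on-label, off-label and potential off-label status from age and recorded COPD or asthma diagnosis alone. Annex Table 1-6 plays no part in that step, nor in cohort entry. In the main table it affects only how the potential off-label group is described.

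**4. Size of the look-back question.** The documents give no count of prior same-substance users, so this is an illustration. Let *s* be their share of the cohort, *q* their off-label proportion and *p* that of all other starters:

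observed = (1 − s) × p + s × q

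With p = 20% and q = 2% (assumed):
- s = 2%: 0.98 × 20 + 0.02 × 2 = 19.6%
- s = 10%: 0.90 × 20 + 0.10 × 2 = 18.2%
- s = 15%: 0.85 × 20 + 0.15 × 2 = 17.3%

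With p = 10%, s from 5% to 30% and q from 0% to 10% (assumed), the result lies between 0.70 × 10 + 0.30 × 0 = 7.0% and 10.0%.

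**5. Against the plan's own precision.** Protocol Table 9 is reproduced in all 20 cells by exact Clopper-Pearson limits, the method named in SAP 7.5.1. At 10% prevalence it gives 6.8 to 14.0 for 300 patients and 8.7 to 11.4 for 2,000. A fall from 10% to 7.0% stays inside the first interval; 8.0% (s = 20%, q = 0) is outside the second. The same method at 20% gives 15.6 to 25.0 (300), 17.3 to 22.9 (800) and 18.3 to 21.8 (2,000). So 18.2% lies inside the first two and just outside the third.

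**The case against.** A reader might infer that prior users of the substance bias the primary outcome, and that they enter because the annex lacks a LABA/LAMA class. The documents do not support either step.

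- The stated aim is to characterise use of the single-agent products in regular practice. A first single-agent dispensing after a combination is a real start of the studied product, and its label status is still decided correctly by age and diagnosis. The shifts in step 4 of the working are bias only if the target were starters of the substance, which the plan does not say.
- Entry follows from 6.3 alone, as step 3 shows.
- The closing words of the 6.3 criterion have no stated object. The single-agent reading is the natural one and the only one the listed codes implement, but Protocol 9.2.3 also speaks simply of a first record for olodaterol or indacaterol.
- Neither document names a marketed combination containing either LABA. The repeated single-agent wording only implies that other formulations exist.
- The profile review in SAP 5.1 lists dispensings and could bring prior combination use to light. Database-specific definitions sit in SAP Section 9.2, which is not in the public text and may contain further rules.
- The date in the annex source line does not prove the age of the list. The SAP annex gives R03AK06 to R03AK12 for LABA/ICS, whereas the protocol annex, under the same source line, says such codes were not available. The list was at least partly revised.

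Most of this stands, and it removes any claim of demonstrated bias in the off-label proportion. It does not rescue the code lists. The profile review covers up to 100 users per drug and is aimed at the COPD and asthma algorithms. The annex footnote on national drug codes helps only for medications that are listed. Whatever the list's date, LABA/LAMA and R03AC19 are not in it.

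**Conclusion.** The code-list point holds on the text. Section 5.1 and the Table 7 footnote call for drugs that Annex Table 1-6 does not contain, and 6.5 turns the omission into non-exposure. Where LABA/LAMA combinations were dispensed, severity and prior respiratory treatment are understated, the residual row without probable COPD is inflated, and some patients are wrongly LABA-naïve. How many patients this affects depends on the use of such products in the study countries, which the documents do not give, and on Section 9.2 containing no correction.

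The look-back in 6.3 needs clarifying; it is not a demonstrated error. Its effect on the off-label proportion cannot be computed from the documents. The ranges in the working rest entirely on assumed shares and rates. Mandatory exclusion of prior same-substance users would change the population studied and is not justified.

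**What to change.** **Code lists.** Add a LABA/LAMA fixed-combination class and R03AC19 to Annex Table 1-6. Carry the class into the probable COPD definition (5.1), the bronchodilator classes (5.3.3) and the LABA list behind the LABA-naïve/switcher split. Update the list to an ATC index that covers the last data year, and correct the source line. List indacaterol with the LABAs in the same revision.

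**Split.** Say where a patient goes whose only recent LABA was the index substance in a combination. Once the class is coded, Protocol 9.2.3 makes that patient neither LABA-naïve nor a switcher.

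**Section 6.3.** State whether the look-back refers to the single-agent product or to every product containing the substance. Keep patients with prior same-substance combination use in the cohort, report their number, and show the off-label proportion without them as a sensitivity analysis.

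**Cost.** Code-list work in each database and one extra table row. The main cohort does not shrink, because no one is excluded from it.

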6.5 HANDLING OF MISSING DATA AND OUTLIERS

The extent of missing data will be evaluated and described. Due to the nature of this study, no imputation of missing data is planned. Missing values are expected in some sociodemographic variables depending on the definition used and in variables related to exposure characterisations such as strength or daily dose. Degree of missingness will depend on the database, and some data sources will have variables that are not available, such as oxygen therapy in PHARMO and hospitalisations in IMS RWE LPD. Diagnoses, prescriptions, and dispensings can be identified in the databases only if they are recorded. Thus, all patients with a certain diagnosis/dispensing in the database will be coded as having

Proprietary confidential information © 2017 Boehringer Ingelheim International GmbH or one or more of its affiliated companies

the respective condition/exposure to the respective drug. All others will be coded as not having the disease/not being exposed to the drug. Therefore, uncoded diagnoses/dispensings may result in misclassification and not in missing values.

6.6 BASELINE, TIME WINDOWS, AND CALCULATED VISITS

The baseline or maximum lookback time period is defined as the period of continuous registration from enrolment up to the index date. Definition of the baseline period overall and the study period in each data source have been provided in [Table 1](#).

The analyses performed in this study will describe off-label use and patient characteristics based on information at baseline; no exposure time windows of risk after the index date will be defined in this study.

Due to the observational and retrospective nature of this study, no mandated visits of patients to health care practitioners are required. Therefore, calculated study visits are not applicable.

7. PLANNED ANALYSIS

The different research centres will use the core final study protocol and SEAP to conduct analyses in the respective data sources and generate output that will be provided to the coordinating centre (RTI Health Solutions), which will generate the study reports.

All the analyses will be conducted separately for olodaterol and indacaterol new users and further stratified by LABA-naïve patients and switchers. Analysis for each report (i.e., interim and final) will include data on all patients starting treatment with olodaterol or indacaterol from the start of such treatment during the study period up to the latest available data (see anticipated study periods for interim and final reports in [Table 1](#)). The interim analysis will include all the analyses described in the present section.

Tables and figure shells describing all planned analyses have been developed (see separate Word file) and will be adapted to each data source. For each data source, an attrition table will be generated to describe the impact on the study size at each step of applying the study inclusion and exclusion criteria (Figure Shell 1).

7.1 DEMOGRAPHIC AND OTHER BASELINE CHARACTERISTICS

7.1.1 Demographic and lifestyle characteristics of new users at the index date

The absolute and relative frequency (i.e., count and percentage) of new users of olodaterol and indacaterol will be presented overall and by calendar year (Shell Table 1); mean, standard deviation, and median and interquartile range of duration of prior enrolment before the index date, daily doses and number of packages of the index prescription (if available) will also be provided.

Distribution of new users by age and sex, overall and by calendar year, for the study medications will be presented. Absolute and relative frequencies, mean, standard deviation, and median and interquartile range will be provided (Shell Table 2.1-2.5).

Lifestyle characteristics, as defined in Section [5.1](#), will be presented by each index medication for the overall population (Shell Table 3.1), for adults (Shell Table 3.2), and for those patients aged 40 years or older with a diagnosis of COPD (Shell Table 3.3). Frequencies will be reported for categorical variables, and mean, standard deviation, median, interquartile range, and minimum and maximum will be reported for continuous variables. The specific characteristics reported within this table (e.g., smoking history and obesity or weight or body mass index) will depend on data availability in each data source.

